5.2. Calculation of Treatment Start Dates, Cycles, and Treatment End dates

Treatment will commence on Day 1 and planned cycle lengths are 28 days. Day 1 of treatment is defined as the first day of study drug. Day 1 of a cycle is defined as day 1 of study drug for the given cycle as recorded on the eCRF.

Cycle end dates are defined as the day before Day 1 of the following cycle. The treatment end date, and the end date of the last cycle, will be calculated as follows:

- For subjects who discontinue prior to the clinical cutoff date, treatment end date is the date of treatment discontinuation from the treatment disposition page in the eCRF;
- For subjects who are still on treatment at the time of study closure or clinical cutoff, the last date of planned cycle (27 days after first dose of the last cycle) will be used as the treatment end date.

The cycle number for each date of interest, e.g. Adverse Event (AE) start date, will be calculated based on the cycle window set by their start and end dates.

The following rules will be implemented for cycle calculations for Treatment-Emergent AEs (TEAEs):

- TEAEs present on or after Day 1 Cycle *i* but before Day 1 of the subsequent Cycle belong to Cycle *i*;
- All TEAEs which occur after Day 1 of the last cycle will be included only in the last cycle.

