10.7.2. Adverse Events

Adverse events will be coded according to the Medical Dictionary for Regulatory Activities (MedDRA) (updated version). The severity of AEs will be graded according to the NCI-CTCAE (version 4.03, June 2010).

Treatment-emergent adverse events are defined as any AE occurring or worsening on or after the first treatment of the study medication and within 28 days after the last dose. All TEAEs, AEs leading to study medication discontinuation, AEs leading to dose reduction/interruption, AEs related to the lenalidomide, SAEs and AE leading to death will be summarized by cycle and 28-day period after last cycle as well as by subject (worse recorded grade) per event type (organ class and preferred term) and grade. A summary of AEs with NCI-CTCAE Grade 3 or higher, as well as the most frequent preferred terms will also be provided by grade and term.

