An external independent data monitoring committee (DMC) will evaluate safety and treatment efficacy data in an ongoing, periodic manner to assess benefit-to-risk considerations throughout the study. The function of the DMC is to monitor the safety and activity of the study treatment. After 4 subjects have completed at least 1 cycle of study treatment, the DMC will evaluate the safety data and provide a recommendation. The DMC will also provide recommendations about the continuation of the study from Stage 1 to Stage 2 (continue as planned, continue with modifications or stop treatment and/or enrollment) and advise on ways to improve quality. The DMC responsibilities, authorities, and procedures will be documented in the DMC charter, which will be endorsed by the DMC prior to the first data review meeting.

The study will consist of 3 phases: Screening Phase, Treatment Phase and Follow-up Phase.

The study will be conducted in compliance with International Conference on Harmonisation (ICH) Good Clinical Practices (GCPs).

Screening Phase

The Screening Phase will start from the time of signing the informed consent form (ICF)/informed assent form (IAF) and will last no more than 14 days, at which time the

Treatment Phase will begin (Cycle 1 Day 1). Subject's screening procedures are to occur during the Screening Phase within 14 days prior to dosing on Cycle 1 Day 1.

Treatment Phase

The lenalidomide dose will be calculated based on body weight. The starting dose will be 2 mg/kg/day with a maximum dose of 70 mg/day. Subjects enrolled in the study will receive lenalidomide for the first 21 days of each 28-day treatment cycle for up to a maximum of 12 cycles of study treatment. After the completion of 12 cycles of study treatment, subjects who demonstrate clinical benefit (CR/CRi/PR) or resistant disease as per the Investigator may continue to receive lenalidomide in an OEP until they meet the criteria for study discontinuation.

In the event of a specific protocol-defined toxicity, no more than 2 dose reductions will be allowed to doses of 1.4 mg/kg/day (not exceeding 50 mg/day) and 1 mg/kg/day (not exceeding 35 mg/day). The dose will not be re-escalated once it has been reduced. Subjects who do not tolerate the minimum dose level of 1 mg/kg/day (not exceeding 35 mg/day) will be discontinued from the study.

Follow-up Phase

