11.1. Adverse Events

Adverse Events will be coded according to MedDRA dictionary version 18.0 or higher. The severity of AEs will be graded according to the National Cancer Institute Common Terminology Criteria for Adverse Events (NCI CTCAE) (version 4.03, May 2009), except for tumor flare reaction, which is defined using CTCAE version 3.

All AEs will be recorded by the Investigator from the time the subject signs the ICF/IAF until 28 days after the last dose of lenalidomide and those SAEs made known to the Investigator at any time thereafter that are suspected of being related to lenalidomide.

In the occurrence of partial dates, refer to Appendix 18.4 where the date imputation guideline is located.

Treatment-emergent adverse events (TEAEs) are defined as any AE occurring or worsening on or after the first treatment of the IP and within 28 days after the last dose administration date. All TEAEs, AEs leading to IP discontinuation, AEs leading to dose reduction/ interruption, AEs related to lenalidomide, and SAEs and AEs leading to death will be summarized by cycle up to a 28-day period after last cycle (see section 5.2), as well as by subject worst recorded grade per event type, SOC, PT and grade. A summary of AEs with NCI CTCAE v 4.0 Grade 3 or higher (except for tumor flare reaction, which is defined using CTCAE version 3), as well as the most frequent PTs, will also be provided by grade and PT. If a subject experiences the same AE more than once with different severity grade, then the event with the highest grade will be tabulated in “by grade” tables. If a subject experiences multiple AEs under the same PT/SOC, then the subject will be counted only once for that PT/SOC. In addition, AEs with a missing intensity will be presented in the summary table as an intensity category of “Missing”.

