11.1.2. TEAEs by System Organ Class and Preferred Term

The incidence of TEAEs will be summarized by MedDRA SOC and PT. The intensity of AEs will be graded 1 to 5 according to the NCI CTCAE.

Tables summarizing the incidence of TEAEs will be generated for each of the following:

- All TEAEs;
- All TEAEs with CTCAE grades 3 or 4;
- All TEAE by CTCAE grade;
- TEAEs reported as treatment-related;
- Treatment-related CTCAE grade 3 or 4 TEAEs;
- Treatment-related CTCAE grade 3 or 4 TEAEs by CTCAE grade;
- CTCAE grade 5 TEAEs;
- Serious TEAE;
- TEAEs leading to death
- Treatment-related serious TEAEs;
- Serious TEAEs leading to discontinuation of lenalidomide
- TEAEs leading to discontinuation of lenalidomide
- TEAEs leading to dose reduction;
- TEAEs leading to dose interruption;
- TEAEs by cycle;
- TEAEs with CTCAE grade 3 or 4 by cycle;
- Non-treatment emergent AEs.

Frequency distributions for shift from baseline to the maximum CTCAE grade during treatment period will be presented for all grades and focusing on grade 3 or 4.

System organ classes are sorted by descending order of frequency of SOC, and by descending order of frequency of PT within SOC, according to the overall column. In tables where the two treatment periods and the overall period are reported, the sorting order will be defined on the basis of frequencies found in the overall column.

For all tables showing results by cycle, OEP and 12th cycle will be considered as a unique cycle labelled “Cycle 12 and higher”.

Listing of AE, SAE, SAE of special interest and AE leading to treatment discontinuation will be provided in separated displays.

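### By-cycle TEAE tables put the post-treatment follow-up into each subject's last cycle and pool Cycle 12 with the whole extension, so the columns cover unequal observation windows

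*SAP*

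**What the plan says.** Protocol 10.7.2 states that adverse events "will be summarized by cycle and 28-day period after last cycle as well as by subject". It names two kinds of period: the cycles, and the 28 days that follow the last one.

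SAP 11.1 words this differently: events "will be summarized by cycle up to a 28-day period after last cycle", with a pointer to SAP 5.2. SAP 5.2 then allocates TEAEs to cycles. For a cycle that is not the last, "Cycle end dates are defined as the day before Day 1 of the following cycle". For the last cycle, "All TEAEs which occur after Day 1 of the last cycle will be included only in the last cycle". SAP 11.1 defines a TEAE as "any AE occurring or worsening on or after the first treatment of the IP and within 28 days after the last dose administration date", so the allocation to the last cycle runs on into the follow-up after treatment.

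SAP 11.1.2 adds that, in every table by cycle, "OEP and 12th cycle will be considered as a unique cycle labelled “Cycle 12 and higher". Under SAP 4.1 and protocol Appendix L, the OEP continues until the subject meets the criteria for study discontinuation. No fixed length is given.

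SAP 16 lists changes from the protocol's statistical section, among them a new denominator for the response rate by cycle. It does not list this change. It drops several adverse event tables, but not TEAEs by cycle or Grade 3 or 4 TEAEs by cycle, so both will be produced.

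**The concern.** A by-cycle table is read as a time course: the reader compares one cycle with the next to see whether toxicity rises or falls. That comparison needs each column to cover a similar length of observation. Here a subject's last cycle is observed for longer than the others, and the final column has no set length.

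The extra time is not spread evenly. It falls on the cycles in which subjects stop. Protocol 8.2.1 makes the end of Cycle 4 a point at which subjects without clinical benefit leave treatment, so incidence in Cycle 4 could appear to rise at a constant daily hazard. Events from weeks off drug would also carry a cycle label.

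Nothing in the tables corrects for this. Neither document states the denominator of the by-cycle adverse event tables. The only exposure-based rate in the SAP is for second primary malignancies (SAP 11.3), and SAP 16 drops those tables.

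**Working it through.** **Inputs.** Cycle length: "planned cycle lengths are 28 days" (SAP 5.2). Dosing: "lenalidomide for the first 21 days of each 28-day treatment cycle" (SAP 4.1). TEAE window: to the last dose plus 28 days (SAP 11.1). Maximum delay of a cycle start: 14 days (SAP 9.7). The documents give no adverse event rate, so the incidences below are assumptions.

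**The plan's own figure.** SAP 9.7 says Cycle 2 should start no later than 42 days after Day 1 of Cycle 1. This reproduces: 28 + 14 = 42. A non-final cycle is therefore 28 days as planned and up to 42 with the allowed delay.

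**Last-cycle window, once treatment has ended.** Window = cycle day of last dose + 28.

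| Last dose on cycle day | Window (days) | Ratio to 28 |
|---|---|---|
| 1 | 29 | 1.04 |
| 7 | 35 | 1.25 |
| 14 | 42 | 1.50 |
| 21 | 49 | 1.75 |

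**Cycle 12 and higher.** With k extension cycles, the last of them fully dosed, window = 28k + 49 days.

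| k | Window (days) | Ratio to 28 |
|---|---|---|
| 0 | 49 | 1.75 |
| 1 | 77 | 2.75 |
| 3 | 133 | 4.75 |
| 6 | 217 | 7.75 |
| 12 | 385 | 13.75 |

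**Effect on the percentage of subjects with an event.** Assume a constant hazard with incidence p per 28 days. Incidence over w days = 1 − (1 − p)^(w/28).

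| Assumed p | 49 days | 133 days |
|---|---|---|
| 10% | 16.8% | 39.4% |
| 20% | 32.3% | 65.4% |
| 30% | 46.4% | 81.6% |
| 50% | 70.3% | 96.3% |

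**A mixed cycle.** If a share s of subjects is in the last cycle, displayed incidence = (1 − s)p + s[1 − (1 − p)^(w/28)]. With p = 20% and s = 40%:

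- last dose on Day 21 (49 days): 0.6 × 0.200 + 0.4 × 0.323 = 24.9%
- last dose on Day 14 (42 days): 0.6 × 0.200 + 0.4 × 0.284 = 23.4%
- last dose on Day 7 (35 days): 0.6 × 0.200 + 0.4 × 0.243 = 21.7%

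With equal 28-day windows the cycle would show 20%. With p = 50%, s = 40% and full dosing, it shows 0.6 × 0.500 + 0.4 × 0.703 = 58.1%.

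**The case against.** Several points on the other side stand.

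- **A reader might infer that a whole extra month is added to every child's last cycle.** It is not. The 28 days run from the last dose, and Days 22 to 28 are off drug in every cycle, so the excess over a 28-day cycle is 1 to 21 days. For a subject still on treatment at the primary cutoff, the rule adds nothing yet.
- **A reader might scale event counts by window length.** With shares of 20%, 40% or 60% in a last cycle, that gives increases of 15%, 30% or 45% (28(1 − s) + 49s = 32.2, 36.4 or 40.6 days, over 28). These are upper bounds. They assume every subject who stops took all 21 doses. At s = 40%, a last dose on Day 7 or Day 14 gives 10% or 20% instead of 30%. The planned tables also show subjects, each counted once per term (SAP 5.1 and 11.1), so percentages rise less than counts.
- **The windows would not be equal even without this rule,** because a delayed non-final cycle may last 42 days.
- **A reader might call this a direct breach of the protocol.** Protocol 10.7.2 names the post-treatment period but fixes no table layout. A separate column is the natural reading, not an explicit requirement.
- **Fixed and extension periods are already reported separately** under SAP 11. That offsets part of the Cycle 12 pooling, though it does not separate the post-treatment weeks.
- **Little depends on these tables.** The analyses are descriptive, the GVHD stopping rule counts subjects rather than cycles, and SAP 14 names no by-cycle adverse event table at the interim.

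None of this removes the unequal windows or the missing declaration in SAP 16.

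**Conclusion.** The concern holds within limits. The SAP's allocation rule lengthens a completed last cycle to 29 to 49 days, against a planned 28 (up to 42 with delay), and leaves the last column open-ended. The SAP does not declare this departure from the period that the protocol names.

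The size depends on how many subjects stop in a cycle and on which day. The illustration of 24.9% instead of 20% rests on an assumed 20% incidence per 28 days, a hazard that is constant on and off drug, no cycle delays, 40% of subjects in their last cycle, and full dosing. Mid-cycle stopping makes it smaller.

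A reader might infer that the trial's safety findings as a whole are biased. The documents do not support that. Overall TEAE tables and the fixed and OEP period summaries are unaffected. What can mislead is the pattern across cycles in two sets of descriptive tables. The change is worth making because it is cheap and uses dates already collected.

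**What to change.** In SAP 5.2 and 11.1.2:

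1. End the last cycle at its planned Day 28 and show later TEAEs in a separate post-treatment column, in line with protocol 10.7.2.
2. Show the OEP apart from Cycle 12 in the by-cycle tables.
3. State that the denominator is the subjects starting the cycle.
4. Add events per 28 subject-days beside each percentage.

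Item 4 is needed because item 1 does not fully equalise the windows. A subject whose last dose is on Day 3 has a TEAE window ending on Day 31: 25 off-drug days stay in the cycle and 3 move to the new column. The post-treatment column itself will cover 1 to 21 days, and delayed cycles remain longer than 28.

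If the sponsor keeps the present rule, it should be declared in SAP 16 and footnoted on each by-cycle table.

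The cost is revised SAP wording and a few extra table columns. No new data are needed.

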5.3. Study Population Definitions

5.3.1. Informed Consent/Assent Population

Informed consent/assent population will consist of all subjects with signed informed consent/assent.

5.3.2. Response Rate Population

The response rate (RR) population shall consist of all subjects classified as evaluable for the primary endpoint, ie, all subjects fulfilling the eligibility criteria, having received at least one dose of the lenalidomide and having at least one disease IWG response assessment post

enrollment or having treatment failure (as assessed in the “Disposition - Treatment” eCRF page) before an assessment can be conducted. The RR population shall be applied to the analysis of the primary endpoint.

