4. OVERALL STUDY DESIGN

4.1. Study Design

This is a multicenter, open-label, single-arm, Phase 2, Simon's Optimal two-stage design study, with an Optional Extension Phase (OEP), that will assess the activity, safety and PK of lenalidomide in pediatric subjects from 1 to ≤ 18 years of age with second or greater rAML. A total of 43 evaluable subjects (18 subjects in Stage 1 and an additional 25 subjects in Stage 2) are required for assessment of the primary endpoint. To allow for subjects found to be unevaluable for the primary endpoint due to an incorrect diagnosis, not having a disease assessment post screening, or who discontinued prior to receiving lenalidomide, up to 4 additional subjects may be enrolled for a maximum of 47 evaluable subjects across approximately 70 sites. Approximately 50% of enrolled subjects will be younger than 12 years of age to provide adequate PK data for this age subset.

If during Stage 1, at least 3 of 18 subjects achieve a morphologic complete response (either CR or CRi) within the first 4 cycles of study treatment, then the study will proceed to Stage 2; otherwise, the study will be terminated. Similarly, if at the final analysis, at least 8 of 43 evaluable subjects across Stages 1 and 2 achieve a response (CR/CRi) within the first 4 cycles of study treatment, it will be concluded that lenalidomide has sufficient activity in pediatric AML to warrant subsequent study.

Morphological response will be assessed using the modified AML International Working Group (IWG) criteria (Cheson, 2003) (Appendix D).

The OEP will allow subjects who demonstrate clinical benefit, as assessed by the Investigator at the completion of 12 cycles of lenalidomide therapy, to continue receiving oral lenalidomide until they meet the criteria for study discontinuation. In the OEP, only safety, dosing, concomitant medications/procedures, and second primary malignancies (SPMs) will be monitored (Table 2).

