10.2. Study Population Definitions

Response Rate population

The response rate (RR) population shall consist of all subjects classified as evaluable for the primary endpoint, ie, all subjects fulfilling the eligibility criteria, having received at least one dose of the lenalidomide and having at least one disease assessment post enrollment or having treatment failure before an assessment can be conducted. The RR population shall be applied to the analysis of the primary endpoint.

Intention to treat population

The intention to treat (ITT) population shall consist of all enrolled subjects regardless of whether they received lenalidomide. The ITT population shall be applied to all treatment activity-based primary and secondary endpoints.

Safety population

The safety population consists of all subjects receiving at least one dose of lenalidomide and shall be applied to all safety based endpoints.

Pharmacokinetic population

The PK population consists of all subjects receiving at least one dose of lenalidomide and having at least one measurable lenalidomide concentration.

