10.3. Sample Size and Power Considerations

Under Simon's Optimal two stage design with a 5% significance level and 80% power, assuming a lower boundary of interest in the response rate of 10% and an upper boundary of interest in the response rate of 25%, a total of 43 evaluable subjects are required for the evaluation of the primary endpoint; 18 in Stage 1 and an additional 25 in Stage 2.

If less than 3 of 18 evaluable subjects in Stage 1 achieve a morphologic response (either CR or CRi) within a maximum of 4 cycles then the study will terminate, otherwise the study shall continue as planned and enrollment of an additional 25 subjects shall continue into Stage 2.

If, at the final analysis, less than 8 of 43 evaluable subjects in both Stage 1 and 2 achieve a response (either CR or CRi) within a maximum of 4 cycles then it will be concluded that lenalidomide, at the dose level tested, does not have sufficient activity in pediatric AML (second

or greater relapse or refractory). However, should at least 8 of the 43 evaluable subjects achieve a response (either CR or CRi) then it will be concluded that lenalidomide, at the dose level tested, demonstrates activity in pediatric subjects with AML (second or greater relapse or refractory) to allow further investigation. Up to 4 additional subjects may be included to account for subjects found to be unevaluable for the primary endpoint (eg, incorrect diagnoses, not having a disease assessment post screening, or who discontinued prior to receiving lenalidomide therapy). The first 43 subjects enrolled and evaluable for the primary endpoint analysis will be used to assess the primary endpoint.

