10.6. Efficacy Analysis

10.6.1. Primary endpoint

Morphologic complete response rate (CR or CRi) rate within 4 investigational product cycles

The primary endpoint is the morphological complete response rate within a maximum of 4 cycles of treatment. Morphological complete response is defined as CR or CRi. These response criteria will be assessed according to the revised AML IWG Criteria (Cheson, 2003).

The morphological complete response rate is defined as the total number of subjects with morphological complete response observed within the first 4 cycles of study therapy (regardless of whether the CR/CRi is observed at the end of Cycle 1, 2, 3 or 4) over the total number of subjects evaluable for this endpoint (maximum likelihood estimator). The CR/CRi does not need to be present at the end of Cycle 4 if observed before this time for the subject to be considered as having achieved a complete response with regards to the primary endpoint. The corresponding Clopper Pearson 95% confidence interval will be calculated for the response rate. The primary analysis of this endpoint will be based upon the ITT population and the Response Rate population. Decision making with regard to continuation to Stage 2 and at the end of Stage 2 will be based on responses within the Response Rate population.

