4. INVESTIGATIONAL PLAN

4.1. Overall Study Design and Plan

This is a multicenter, open-label, single-arm, Phase 2, Simon's Optimal two-stage design study, with an Optional Extension Phase (OEP), that will assess the activity, safety and PK of lenalidomide in pediatric subjects from 1 to ≤ 18 years of age with second or greater rrAML. A total of 43 evaluable subjects (18 subjects in Stage 1 and an additional 25 subjects in Stage 2) are required for assessment of the primary endpoint. To allow for subjects found to be unevaluable for the primary endpoint due to an incorrect diagnosis, not having a disease assessment post screening, or who discontinued prior to receiving lenalidomide, up to 4 additional subjects may be enrolled for a maximum of 47 evaluable subjects across approximately 75 sites. Approximately 50% of enrolled subjects will be younger than 12 years of age to provide adequate PK data for this age subset.

If during Stage 1, at least 3 of 18 subjects achieve a morphologic complete response (either CR or CRi) within the first 4 cycles of study treatment, then the study will proceed to Stage 2; otherwise, the study will be terminated. Similarly, if at the primary final analysis, at least 8 of 43 evaluable subjects across Stages 1 and 2 achieve a response (CR/CRi) within the first 4 cycles of study treatment, it will be concluded that lenalidomide has sufficient activity in pediatric acute myeloid leukemia (AML) to warrant subsequent study.

Morphological response will be assessed using the modified AML International Working Group (IWG) criteria ([Cheson, 2003](#)) (section 18.1).

The OEP will allow subjects who demonstrate clinical benefit, as assessed by the Investigator at the completion of 12 cycles of lenalidomide therapy, to continue receiving oral lenalidomide until they meet the criteria for study discontinuation. In the OEP, only safety, dosing, concomitant medications/procedures, and SPMs will be monitored.

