4.4. Sample Size Determination

Under Simon's Optimal two stage design with a 5% significance level and 80% power, assuming a lower boundary of interest in the response rate of 10% and an upper boundary of interest in the response rate of 25%, a total of 43 evaluable subjects are required for the evaluation of the primary endpoint; 18 in Stage 1 and an additional 25 in Stage 2.

If less than 3 of 18 evaluable subjects in Stage 1 achieve a morphologic response (either CR or CRi) within a maximum of 4 cycles then the study will terminate, otherwise the study shall continue as planned and enrollment of an additional 25 subjects shall continue into Stage 2.

If, at the primary final analysis, less than 8 of 43 evaluable subjects in both Stage 1 and 2 achieve a response (either CR or CRi) within a maximum of 4 cycles then it will be concluded that lenalidomide, at the dose level tested, does not have sufficient activity in pediatric AML (second or greater relapse or refractory). However, should at least 8 of the 43 evaluable subjects achieve a response (either CR or CRi) then it will be concluded that lenalidomide, at the dose level tested, demonstrates activity in pediatric subjects with AML (second or greater relapse or refractory) to allow further investigation. Up to 4 additional subjects may be included to account for subjects found to be unevaluable for the primary endpoint (eg, incorrect diagnoses, not having a disease assessment post screening, or who discontinued prior to receiving lenalidomide therapy). The first 43 subjects enrolled and evaluable for the primary final analysis will be used to assess the primary endpoint.

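### The replacement wording calls any child without a post-screening assessment unevaluable, and does not except the treated early failures that the Response Rate definition keeps in the decision denominator

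*SAP*

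**What the plan says.** **Who is evaluable.** Protocol 10.2 puts an eligible, treated child in the Response Rate (RR) population on the condition of "having at least one disease assessment post enrollment or having treatment failure before an assessment can be conducted". SAP 5.3.2 keeps this rule but names a data source for the second route: "having treatment failure (as assessed in the “Disposition - Treatment” eCRF page) before an assessment can be conducted".

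**Which population decides.** Protocol 10.6.1 says that the decision to continue to Stage 2 and the decision "at the end of Stage 2 will be based on responses within the Response Rate population". SAP 14 ties the Stage 1 look to the same population. Protocol 10.3 fixes the final count: "The first 43 subjects enrolled and evaluable for the primary endpoint analysis will be used to assess the primary endpoint". The ITT population is also used for the primary analysis (Protocol 10.6.1, SAP 10.1), but no decision rule is attached to it.

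**Who may be replaced.** Protocol 4.1 allows extra enrolment for subjects "unevaluable for the primary endpoint due to an incorrect diagnosis, not having a disease assessment post screening, or who discontinued prior to receiving lenalidomide". The Protocol Summary (Study Design), Protocol 7.1 and 12.2, and SAP 4.1 say the same. Protocol 10.3 gives the list as examples: "unevaluable for the primary endpoint (eg, incorrect diagnoses, not having a disease assessment post screening, or who discontinued prior to receiving lenalidomide therapy". The Protocol Summary (Statistical Methods) and SAP 4.4 follow that form. This makes eight places in all. SAP 4.4 states the allowance as "Up to 4 additional subjects may be included to account for subjects found to be unevaluable for the primary endpoint"; SAP 4.1 states it as "up to 4 additional subjects may be enrolled for a maximum of 47 evaluable subjects".

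**What counts as treatment failure.** Protocol Appendix D and SAP 18.1 include death within 7 days of therapy, some later deaths without a marrow examination, and failure to complete the first course. The reasons that SAP 6 lists for the Disposition - Treatment page, and those in Protocol 12.1, include death, adverse event, withdrawal, physician decision and other. Neither list has a treatment failure item.

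**The concern.** A dosed, eligible child who dies before the first scheduled marrow (Day 22 to 27 of Cycle 1) fits both rules. Under the RR definition the child is a non-responder in the denominator. Under the replacement list the child has no post-screening assessment, and so is unevaluable and replaceable. The list names undosed subjects separately, so the no-assessment ground is not confined to children who were never treated.

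The SAP adds a second route to the same result. It finds these failures through a page whose listed reasons do not include treatment failure, and it does not say which reasons qualify. A programmer who applied SAP 5.3.2 literally could find no child who meets the clause.

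In either case, certain non-responders would leave the denominator of a single-arm response rate and be replaced by children who can still respond. That favours a go decision at both stages, in a design whose exact type I error is only 0.2 percentage points below its 5% ceiling.

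**Working it through.** **Inputs** (Protocol 10.3, SAP 4.4): p0 = 0.10, p1 = 0.25; 18 subjects in Stage 1 and 25 in Stage 2; continue at 3 or more of 18; conclude activity at 8 or more of 43; up to 4 extra subjects.

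**1. The plan's own figures.** With X ~ Bin(18, p) and Y ~ Bin(25, p),

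P(conclude activity) = Σ over x ≥ 3 of P(X = x) · P(Y ≥ 8 − x).

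- At p = 0.10: P(X ≤ 2) = 0.150 + 0.300 + 0.284 = 0.734, so P(proceed) = 0.266. The terms for x = 3 to 8 are 0.01646, 0.01655, 0.01008, 0.00382, 0.00093 and 0.00015. Alpha is therefore 0.0480.
- At p = 0.25: power = 0.8003.

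A search over designs with alpha ≤ 0.05 and power ≥ 0.80 returns the same design as the one with the smallest expected sample size under p0 (24.7). The stated design is correct.

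**2. If early failures are replaced.** Assume a true rate of 10% among all treated children, and let k1 and k2 be the treated early non-responders replaced in Stages 1 and 2. Two calculations were made with the same cut-offs: (i) stage rates raised to 0.10·(18 + k1)/18 and 0.10·(25 + k2)/25; (ii) responders drawn as Bin(18 + k1, 0.10) and Bin(25 + k2, 0.10).

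| k1, k2 | Alpha (i) | Alpha (ii) |
|---|---|---|
| 0, 0 | 0.0480 | 0.0480 |
| 0, 1 | 0.0525 | 0.0526 |
| 1, 0 | 0.0551 | 0.0554 |
| 0, 4 | 0.0670 | 0.0673 |
| 2, 2 | 0.0741 | 0.0749 |
| 4, 0 | 0.0795 | 0.0809 |

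With one replaced in Stage 1, P(proceed) under p0 rises from 0.266 to 0.294–0.295.

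**3. Check by a different route.** Let a fraction f of treated children be early failures without an assessment, and replace the first four. An exact sequential calculation at p = 0.10 gives alpha 0.053 (f = 2%), 0.061 (5%), 0.071 (10%) and 0.079 (20%). The documents give no value for f, so this range is an assumption.

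**4. Effect on the reported rate.** Replacing k early failures raises the expected rate over the first 43 from p to p·(43 + k)/43, a difference of p·k/43.

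- k = 1: 0.10/43 = 0.23 points; 0.25/43 = 0.58 points.
- k = 4: 0.40/43 = 0.93 points; 1.00/43 = 2.33 points.

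**5. The figure of 47.** 43 evaluable plus 4 places that cover unevaluable subjects gives 47 enrolled. It does not give 47 evaluable.

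**The case against.** The strongest reply is that the documents already settle which rule decides. Protocol 10.2 and SAP 5.3.2 are the formal definition of evaluable and expressly include failure before assessment. Protocol 10.6.1 and SAP 14 base the decisions on that population. The replacement statements only allow extra enrolment for subjects found to be unevaluable, and three of them merely give examples. A treated early failure is evaluable by definition, so is never found to be unevaluable. The no-assessment ground then covers treated children with neither an assessment nor a treatment failure. This is the better reading. What remains is that no section states it, and that the unqualified list stands beside the decision rule itself in Protocol 10.3 and SAP 4.4.

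Three further limits also stand.

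- Enrolling extra children does not by itself remove anyone from the RR population. Alpha moves only if the early failures are also dropped from it.
- The calculation takes 10% among all treated children. If 10% were instead meant for evaluable subjects, with evaluability set by the replacement list, alpha would stay at 0.048 and the issue would be one of selection and estimand.
- Few children are exposed. Protocol 6.22 calls for an IWG assessment at discontinuation, although the marrow may be omitted when peripheral blasts are collected. The ITT analysis keeps these children.

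A reader might infer that the design breaches its 5% level. It does not under the RR definition. A reader might also infer that the case report form cannot record treatment failure. The form is not among the documents, and entries such as death or other could carry these cases; what can be shown is only that the mapping is missing. Finally, a reader might infer that every treated child without an assessment belongs in the RR population. Protocol 10.2 does not say that: it requires an assessment or treatment failure.

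**Conclusion.** The inconsistency in wording is real and should be fixed, because it concerns who counts in the denominator of both decisions. The design itself is sound: alpha is 0.048 and power 0.800 if treated early failures are kept as non-responders, which is how the RR definition is best read.

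The inflation depends on two conditions: that the replacement wording or the literal page reference is applied, and that the true rate is 10% among all treated children. Alpha is then 0.053 to 0.055 with one early failure replaced. The range of 0.067 to 0.081 needs all four slots to be used this way, which is remote because the slots also serve wrong diagnoses and undosed subjects. Confidence is high that the exception and the mapping are missing. Whether any inflation would occur depends on how the text is applied and on the number of early failures, which is not known.

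**What to change.** 1. In all eight replacement statements (Protocol Summary twice, Protocol 4.1, 7.1, 10.3 and 12.2, SAP 4.1 and 4.4) add: *A treated, eligible subject who dies or has treatment failure (Appendix D / SAP 18.1) before an assessment is evaluable, counts as a non-responder and is not replaced.* Keep the no-assessment ground only for treated subjects who do not meet the treatment failure definition.
2. In SAP 5.3.2 define treatment failure by Appendix D / SAP 18.1, and state which disposition entries count (for example death, or discontinuation before the first course is completed). Keep this consistent with Protocol 10.2, so that the two documents still define one population.
3. In the Protocol Summary (Study Design), Protocol 4.1, 7.1 and 12.2, and SAP 4.1, change the maximum from 47 evaluable to 47 enrolled.

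**Cost.** These are text changes; sample size and cut-offs do not move. Compared with replacing such children, the expected reported rate is lower by about 0.2 points per retained early failure at a true rate of 10%, and about 0.6 points at 25%. Power at 25% among all treated children stays at the planned 0.800.
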